12.7.2. Ratio of Natural log (ACR)/eGFR

The ratio of natural log(ACR)/eGFR will be analyzed through Week 16. The MMRM results will be reported by rare CKD cohort. The ratio of natural log(ACR) / eGFR will be the natural log (ACR) and eGFR values collected closest to the target study day (Section 7.3) through the Week 16, and the baseline values are described in Section 7.2.5. The change from baseline in natural log(ACR) / eGFR will be calculated for each time point through Week 16 visit (i.e., Weeks 1, 2, 4, 6, 8, 12, and 16). Missing data will not be imputed. The primary inference will be the test of LS mean at each time point. The estimation method for the model will be restricted maximum likelihood (REML). The SAS pseudo-code is as follows:

[REDACTED]

In the event the MMRM model with an unstructured covariance structure does not converge, the following covariance structures will be as substitution in the following order. Each subsequent covariance structure will be used only if all previous covariance structure(s) is (are) used and the model(s) did not converge.

1. Toeplitz covariance structure (assuming measurements from samples taken closer together in time are more highly correlated than those from samples taken farther apart).
2. First order of auto-regressive [AR(1)] covariance structure (assuming measurements from samples taken closer together in time are more highly correlated than those from samples taken farther apart).
3. Compound symmetry covariance structure (assuming equal correlation for measurements from a patient, regardless of how far apart in time when they were taken).

12.7.3. Change from Baseline in ACR

Within each rare CKD cohort, the change from baseline ACR will be summarized for all patients, as well as by baseline ACR category ($ACR \leq 300$, $ACR > 300$). Summaries of ACR will use the geometric mean with 95% confidence intervals instead of the arithmetic mean, and will display ACR results in units of mg/g. Changes from baseline in ACR will be reported as the post-baseline/baseline ratios and will be summarized by geometric means with 95% confidence intervals at each time point.

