## 5.1.2.6. Increases in Urinary Protein

Increases in urinary albumin have been observed in some patients treated with bardoxolone methyl with chronic kidney disease and type 2 diabetes. The increases are likely due to bardoxolone methyl's pharmacological modulation of tubular protein reabsorption and have not been associated with interstitial fibrosis or injury. In preclinical studies, bardoxolone methyl has been shown to downregulate the primary proteins involved in protein reabsorption in the proximal tubules: the megalin-cubilin complex. Moreover, the magnitude of observed eGFR increases with bardoxolone methyl treatment is thought to reduce the residence time of protein in the proximal tubules, thereby reducing protein reuptake and increasing urinary protein levels. Therefore, increased eGFR, together with decreased megalin expression, is thought to result in decreased fractional absorption of albumin and increased urinary excretion of albumin. Consistent with bardoxolone methyl-mediated protection in preclinical models of protein-overload-induced nephropathy, these pharmacological effects are thought to reduce protein overload and secondary nephropathy caused by excessive albumin uptake and therefore are not associated with tissue injury and interstitial fibrosis.

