## 8. SELECTION AND WITHDRAWAL OF PATIENTS

#### 8.1. Patient Inclusion Criteria

Diagnosis and main criteria for inclusion:

- Male and female patients 18 ≤ age ≤ 60 upon study consent;
- Screening eGFR (average of Screen A and Screen B eGFR values) ≥ 30 and ≤ 90 mL/min/1.73 m². The two eGFR values collected at Screen A and Screen B visits used to determine eligibility must have a percent difference ≤ 25%;
- Albumin to creatinine ratio (ACR) ≤ 2500 mg/g at Screen B visit;
- 4. If receiving an angiotensin converting enzyme (ACE) inhibitor and/or an angiotensin II receptor blocker (ARB), patients should be prescribed the maximally tolerated labeled daily dose (MTLDD), as defined in Section 9.1.7, for at least 6 weeks prior to the Screen A visit. The dosage of ACE inhibitor and/or ARB should remain the same throughout the remainder of the study (i.e., no change in dosage or medication), and any potential changes should be discussed with the medical monitor. Patients not taking an ACE inhibitor and/or ARB because of a medical contraindication may be eligible if they have discontinued treatment at least 8 weeks prior to the Screen A visit (these patients must be discussed with the medical monitor prior to enrollment);
- For patients enrolling in T1D Cohort:
  - Diagnosis of type 1 diabetes confirmed by fasting C-peptide level. Diagnosis must have been made ≤ 35 years of age;
  - Prescribed stable dose of insulin to maintain adequate glucose control for at least 6 months prior to the Screen A visit;
- For patients enrolling in IgAN Cohort:
  - Biopsy-confirmed IgA nephropathy;
- For patients enrolling in FSGS Cohort:
  - Biopsy-confirmed FSGS that is not due to known secondary causes including morbid obesity, decreased renal mass, viral infections, drug-induced nephrotoxicity, or prior history of vasculitis;
- For patients enrolling in ADPKD Cohort:
  - Genetic confirmation of PKD1 mutation;
- Adequate bone marrow reserve and organ function at the Screen A visit as follows:
  - Hematologic: Absolute neutrophil count > 1.5 x 10^3/L, platelets > 100 x 10^3/L, hemoglobin (Hgb) ≥ 9 g/dL;
  - b. Hepatic: Total bilirubin (TBL) ≤ 1.5X the upper limit of normal (ULN), alanine aminotransferase (ALT) and aspartate aminotransferase (AST) ≤ 1.5X ULN;
- Able to swallow capsules;

- Willing and able to comply with scheduled visits, treatment plan, laboratory tests, and other study procedures;

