5.2. Randomization and Dosing

Randomization refers to patients receiving open-label bardoxolone methyl (BARD). All patients will receive BARD throughout the study as described in the protocol with the maximum bardoxolone methyl dose determined by urine albumin-to-creatinine ratio (ACR) at Screen B. The diagram below shows dose titration and maintenance schedules according to the baseline urine albumin-to-creatinine ratio (ACR) ≤ 300 mg/g or >300 mg/g. Patients with macroalbuminuria (300 mg/g $< \text{ACR} \leq 2500$ mg/g) at the Screen B visit will account for up to approximately 50% of patients enrolled within each cohort. Patients with ACR ≤ 300 mg/g at Screen B will be titrated to a maximum dose of 20 mg BARD, and patients with ACR > 300 mg/g at Screen B will be titrated to a maximum dose of 30 mg BARD. Patients will start with once-daily dosing at 5 mg and will dose-escalate to 10 mg at Week 2, to 20 mg at Week 4, and then to 30 mg at Week 6 (only if Screen B ACR >300 mg/g) unless contraindicated clinically and approved by the medical monitor.

Schema for Study of Bardoxolone Methyl in Patients with Rare Chronic Kidney Diseases

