^a Total Screening period should not exceed 6 months.

^b Screen B visit should be no more than 30 days prior to Day 1.

^c Day 1 is the day of administration of the first dose. **On Day 1, all procedures should be performed before study drug administration.**

^d Patients who terminate from the study prior to the Week 12 study visit should be brought back to the clinic as soon as possible for early termination assessments (*i.e.*, end-of-treatment visit) as well as a follow-up visit 4 weeks later.

^e Screening eligibility procedures do not need to be repeated on Day 1; however, a review of any changes in eligibility criteria should be evaluated prior to Day 1 procedures, and a urine pregnancy test should be performed for WOCBP.

^f An echocardiogram performed at the Screen A visit or within 6 months prior to Day 1 may be used to determine eligibility.

^g A serum pregnancy test will be performed at the Screen A visit for WOCBP or at any point in time if a pregnancy is suspected. All other pregnancy assessments will be urine pregnancy tests.

^h AE assessments on Day 1 should be performed following study drug administration.

ⁱ Only patients enrolling in the IgA nephropathy cohort or the FSGS cohort are required to have a kidney biopsy. Patients with definitive diagnosis of IgA nephropathy or FSGS from previous biopsy will not have a kidney biopsy as part of the study, but must provide diagnosis documentation from previous kidney biopsy for eligibility.

^j Only patients enrolling in the T1D cohort are required to have fasting C-peptide levels assessed. Patients should be instructed to fast prior to study visit.

^k Only patients enrolling in the ADPKD disease cohort are required to have genetic testing. Patients with confirmed PKD1 mutations from previous genetic testing will not have genetic testing performed as part of the study, but must provide documentation of genetic mutation for eligibility.

^l Albumin to creatinine ratio will be measured by first morning void spot urine collection. Appropriate containers for the collection will be provided to the patient at the visit prior to collection.

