7.2.4. Albumin/Creatinine Ratio (ACR)

Baseline ACR is defined as the average of Screen B and Day 1 ACR values.

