9.3. Demographics and Baseline Characteristics

Demographics and baseline characteristics will be summarized by rare CKD cohort for the safety analysis set. Demographic characteristics will include age, gender, race, and ethnicity. Baseline ACR will be summarized by baseline ACR values, not the stratification cohort to which a patient was randomized. The baseline characteristics include:

- Baseline weight,
- Height,
- Body mass index (BMI), and BMI category: < 30 , ≥ 30 ,
- Baseline values of eGFR, baseline CKD stage (Stage 3: eGFR 30 to < 60 ; Stage 2: eGFR ≥ 60 to < 90 ; Stage 1: eGFR ≥ 90),
- Baseline serum creatinine,
- Baseline ACR,
- Baseline ACR status (ACR ≤ 300 mg/g; 300 mg/g $<$ ACR ≤ 1000 mg/g; ACR $>$ 1000 mg/g),
- Age of the diagnosis (T1D cohort only)
- C-peptide level (T1D cohort only),
- Prescribed a stable dose of insulin (T1D cohort only), and

- Baseline Angiotensin converting enzyme (ACE)-inhibitor and Angiotensin II receptor blocker (ARB) use:
 - Only ACEi treatment;
 - Only ARB treatment;
 - ACEi and ARB treatment
 - No ACEi or ARB treatment.

The above information will be listed by patient.

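### SAP 12.7.3 sorts patients by the same averaged baseline ACR that it divides by, which gives a false fall above 300 mg/g and a false contrast between the categories

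*SAP*

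**What the plan says.** Three definitions in the SAP combine.

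- Category: in section 12.7.3, within each cohort, "the change from baseline ACR will be summarized for all patients, as well as by baseline ACR category", with the cut at 300 mg/g. Section 9.3 points to the measured value as the classifier: "Baseline ACR will be summarized by baseline ACR values, not the stratification cohort to which a patient was randomized".
- Change: "Changes from baseline in ACR will be reported as the post-baseline/baseline ratios", summarised by geometric means with 95% confidence intervals at each time point.
- Baseline: section 7.2.4 states "Baseline ACR is defined as the average of Screen B and Day 1 ACR values". It names no log scale or geometric mean, so the natural reading is the arithmetic mean of two values.

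On measurement, SAP 5.3 says "Albumin to creatinine ratio will be measured by first morning void spot urine collection". Entry is truncated by "Albumin to creatinine ratio (ACR) ≤ 2500 mg/g at Screen B visit" (Protocol 8.1). SAP 5.2 sets the dose ceiling by the Screen B value alone, and patients above 300 mg/g "at the Screen B visit will account for up to approximately 50% of patients enrolled within each cohort". The trial is single-arm, with about 25 patients per cohort. SAP 12.7 lists the category summary among additional safety endpoints. Neither section 12.7 nor section 12.7.3 mentions regression to the mean.

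**The concern.** When one noisy measurement decides which group a patient joins and is also the denominator of that patient's ratio, the error in it does not average out within groups. Patients placed above 300 mg/g are there partly because their two baseline samples ran high. Later samples do not share that error, so the ratio falls below 1 without any drug effect. A control arm would show the same artefact and allow it to be subtracted, but this trial has none.

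The direction matters. Protocol 5.1.2.6 reports that "Increases in urinary albumin have been observed in some patients treated with bardoxolone methyl", so a rise in ACR is a recognised safety question. The artefact is reassuring in the group with the heavier albuminuria, most of whom have the higher dose ceiling. It also makes the two categories look different when nothing separates them.

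**Working it through.** The documents state no figure for this summary, so there is nothing to reproduce. The check asks what the SAP's definitions return when ACR does not change.

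**Inputs from the documents:** baseline from Screen B and Day 1; cut at 300 mg/g; entry if Screen B ≤2500 mg/g; geometric mean of post/baseline.

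**Assumed, because the documents do not give them:** median ACR 100 or 250 mg/g; between-patient SD of ln ACR τ = 1.0 or 1.4; within-patient SD σ = 0.4, 0.5 or 0.7; independent errors at each visit.

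**Step 1, regression to the mean alone.** Take a geometric baseline G and ignore the entry cap. Then E[ln post − G | G] = −k(G − μ), with k = (σ²/2)/(τ² + σ²/2). For median 250, τ = 1.4, σ = 0.5:

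- k = 0.125/2.085 = 0.060; SD of G = √2.085 = 1.444; standardised cut = ln(300/250)/1.444 = 0.126.
- Above: mean of G − μ = 1.444 × 0.880 = 1.271; ratio = exp(−0.060 × 1.271) = 0.93.
- Below: mean of G − μ = −1.444 × 0.719 = −1.039; ratio = exp(0.060 × 1.039) = 1.06.

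**Step 2, arithmetic baseline under a geometric-mean ratio.** The log of an arithmetic mean of two values exceeds the mean of their logs by about Var(difference)/8 = 2σ²/8 = σ²/4. At σ = 0.5 that is 0.0625, a factor of exp(−0.0625) = 0.94 on every patient's ratio, whatever the category. Combined: above 0.93 × 0.94 = 0.87; below 1.06 × 0.94 = 1.00. The second bias deepens the fall above 300 and cancels the rise below.

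**Step 3, simulation with the entry cap, no true change** (2,000,000 patients per row):

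| Median | τ | σ | Arithmetic >300 | Arithmetic ≤300 | Arithmetic all | Geometric >300 | Geometric ≤300 |
|---|---|---|---|---|---|---|---|
| 100 | 1.0 | 0.4 | 0.853 | 0.984 | 0.962 | 0.888 | 1.020 |
| 100 | 1.0 | 0.5 | 0.784 | 0.977 | 0.943 | 0.835 | 1.032 |
| 100 | 1.0 | 0.7 | 0.641 | 0.968 | 0.896 | 0.721 | 1.065 |
| 100 | 1.4 | 0.4 | 0.895 | 0.984 | 0.964 | 0.931 | 1.022 |
| 100 | 1.4 | 0.5 | 0.845 | 0.979 | 0.947 | 0.899 | 1.035 |
| 100 | 1.4 | 0.7 | 0.725 | 0.965 | 0.902 | 0.816 | 1.066 |
| 250 | 1.0 | 0.4 | 0.900 | 1.018 | 0.965 | 0.935 | 1.055 |
| 250 | 1.0 | 0.5 | 0.853 | 1.031 | 0.948 | 0.905 | 1.085 |
| 250 | 1.0 | 0.7 | 0.749 | 1.072 | 0.910 | 0.834 | 1.167 |
| 250 | 1.4 | 0.4 | 0.924 | 1.004 | 0.969 | 0.961 | 1.041 |
| 250 | 1.4 | 0.5 | 0.884 | 1.010 | 0.953 | 0.939 | 1.065 |
| 250 | 1.4 | 0.7 | 0.797 | 1.026 | 0.918 | 0.890 | 1.127 |

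The >300 group falls in all 12 rows under either baseline. With the arithmetic baseline, the ≤300 group rises in six rows (median 250) and falls in six (median 100). The >300 ratio divided by the ≤300 ratio runs from 0.641/0.968 = 0.66 to 0.924/1.004 = 0.92.

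A wider grid of 27 scenarios (median 100-300, τ 1.0-2.0, σ 0.3-0.7), with the arithmetic baseline, gives 0.64-0.97 above 300 and 0.96-1.10 at or below.

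**Step 4, confidence intervals.** In that wider grid, with 12 patients above 300, the 95% interval lies wholly below 1 in 4.5% to 38% of groups, against a nominal 2.5%. With median 300, τ = 1.5, σ = 0.5 it is 8%. The 38% comes from median 100, where only about 19% of patients exceed 300. That is about 5 of 25, so 12 is generous there.

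**Step 5, the remedy.** Classifying by Screen B and dividing by Day 1 gives 0.998-1.002 in both categories, in these 12 scenarios and in the 27. Changing the classifier alone and keeping the averaged denominator leaves 0.66-0.97 above 300 in the 27.

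**The case against.** The strongest reply is that the table is descriptive. No test or decision hangs on it, and albuminuria is also examined through the all-patient ratio, counts above 3500 mg/g that use no baseline, ln(ACR)/eGFR, and listings. ACR is also measured at Week 16, and under independent errors the artefact is equal at every post-baseline visit, so it cancels when the same patients are compared on and off treatment. All of this stands and limits the consequence, except that the all-patient ratio is itself biased under an arithmetic baseline.

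A second reply is that noise dominates. With 12 patients per category the standard error of the mean log ratio is about σ√1.5/√12, or 0.14 to 0.25 for σ = 0.4 to 0.7. At median 250 and τ = 1.4, the geometric-baseline bias is under half of that: |ln 0.961|/0.14 = 0.28 and |ln 0.890|/0.25 = 0.47. This also stands, but under the arithmetic reading the bias is |ln 0.924|/0.14 = 0.56 to |ln 0.797|/0.25 = 0.91 standard errors.

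A reader might infer three stronger things, none of which the documents support:

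- A mirror-image false rise at or below 300. It needs a geometric baseline, which SAP 7.2.4 does not name. With an arithmetic one the lower group sits near 1 and can fall.
- That the whole fall above 300 is regression to the mean. Part is the arithmetic-denominator bias, which affects every patient.
- That the >300 category is the group titrated to 30 mg. SAP 5.2 sets the ceiling by Screen B alone and the category uses the average. The two differ for about 3% to 14% of patients in the 27 scenarios.

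**Conclusion.** The point holds for the >300 group and for the contrast between categories. Followed as written, SAP 12.7.3 reports a fall above 300 mg/g when nothing has changed: about 0.64-0.92 under the arithmetic reading of baseline, or 0.72-0.96 under a geometric one. At median 250, τ = 1.4 and σ = 0.5, a true rise of 13% (1/0.884) would be shown as no change. At or below 300 the net effect is about 0.97-1.07 (arithmetic) or 1.02-1.17 (geometric), so no direction can be asserted there without settling which average is meant. The all-patient ratio is separately biased to about 0.90-0.97 by the arithmetic baseline.

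All sizes rest on ACR variability that the documents do not supply, and on independent visit errors. The direction above 300 was the same in every scenario tried. The primary eGFR analysis is untouched. This should be corrected because it is a listed safety summary biased in the reassuring direction, but its effect on the trial's conclusions is modest.

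**What to change.** In SAP 12.7.3:

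- Category rows: classify by the Screen B ACR, which SAP 5.2 already uses, and divide by the Day 1 ACR. Both changes are needed.
- All-patient row, and the same ratio in SAP 12.2: define baseline as the geometric mean of Screen B and Day 1. This removes the σ²/4 bias. The entry cap on Screen B still leaves a small upward residual, 1.000 to 1.023 in the 12 scenarios.
- Footnote: state that the category and all-patient rows use different denominators and do not combine to a total.
- State that a patient without a pre-dose Day 1 ACR is left out of the category rows, and give the count.

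Both samples are already scheduled, so the change is wording and programming only. The price is precision: with one baseline sample the log ratio has variance 2σ² in place of 1.5σ², so its standard error rises by √(2/1.5) = 1.15, about 15%. With 12 patients that is roughly 0.16-0.29 in place of 0.14-0.25. The ACR covariate in the eGFR model can stay as it is.

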13. PHARMACOKINETICS ANALYSIS

Blood samples for determination of plasma bardoxolone methyl and potential metabolite concentrations will be drawn as shown in [Table 3](#). The PK profile of bardoxolone methyl will be evaluated from plasma concentration data from individual patients. The PK parameters, such as C_{max} , T_{max} , and AUC_{0-t} will be determined by Reata or a third party vendor. The bardoxolone methyl plasma concentration data, along with PK parameters, will be listed. The PK parameters will be summarized descriptively by rare CKD cohort. Additional analyses and summaries may be performed, if warranted.
